A Phase II Trial of Protease Inhibitor, Nelfinavir (NFV), Given with Definitive, Concurrent Chemoradiotherapy (CTRT) in Patients with Locally-Advanced, Human Papilloma Virus (HPV) negative, Squamous Cell Carcinoma of the Head and Neck

Regulatory Sponsor: [name]
University of Pennsylvania, Department of Radiation Oncology
[name]
[name]
[contact]
[contact]

Sub-Investigators: Radiation Oncology – [name], PhD
Radiation Oncology – [name]
Radiation Oncology- [name]
Radiology – [name]
Radiology – [name], PhD
[name]

Collaborators: Radiation Oncology- [name]
Radiation Oncology- [name]
Medical Oncology – [name]
Medical Oncology – [name], MPH
Medical Oncology- [name]
Otolaryngology – [name], MD
Otolaryngology – [name]
Otolaryngology – [name]
Otolaryngology – [name]
Biostatistician- [name], MS

Study Product: Nelfinavir
¹⁸F-FMISO

Protocol Number: 817878

CONFIDENTIAL

This document is confidential and the property of the University of Pennsylvania. No part of it may be transmitted, reproduced, published, or used by other persons without prior written authorization from the study sponsor.

Table of Contents

STUDY SUMMARY	3
1 INTRODUCTION.....	4
2 STUDY OBJECTIVES.....	6
3 STUDY DESIGN.....	7
4 SUBJECT SELECTION AND WITHDRAWAL.....	8
5 STUDY DRUG	14
6 STUDY PROCEDURES.....	19
7 STATISTICAL PLAN.....	255
8 SAFETY AND ADVERSE EVENTS	27
9 DATA HANDLING AND RECORD KEEPING	33
10 DATA AND SAFETY MONITORING PLAN.....	35
11 ETHICAL CONSIDERATIONS.....	36
12 STUDY FINANCES.....	36
13 PUBLICATION PLAN.....	36
14 REFERENCES.....	37

List of Abbreviations

Chemoradiotherapy:	CTRT
Computed Tomography:	CT
Head and neck squamous cell carcinoma	HNSCC
Nelfinavir:	NFV
Human Papilloma Virus:	HPV
Positron Emission Tomography	PET
Tumor to Muscle Ratio	TM

Study Summary

Title	A Phase II Trial of Protease Inhibitor, Nelfinavir (NFV), Given with Definitive, Concurrent Chemoradiotherapy (CTRT) in Patients with Locally-Advanced, Human Papilloma Virus (HPV) negative, Squamous Cell Carcinoma of the Head and Neck
Short Title	Definitive Nelfinavir with Chemoradiation for Head and Neck Cancer
Protocol Number	817878
Phase	Phase II
Methodology	Open Label
Study Duration	5 years
Study Center(s)	University of Pennsylvania; Philadelphia VA Medical Center
Objectives	To determine locoregional control in patients with locally advanced, HPV-negative head and neck cancer treated with definitive NFV + CTRT.
Number of Subjects	28

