4.7 Study Duration

With an estimated accrual of 7-8 subjects per year, it is anticipated that accrual will continue for approximately 4 years. Patients will then be followed an additional 6 months prior to final statistical analysis.

[figure not shown]
5 Study Drugs

5.1 *Description*

Nelfinavir

There are ample data available regarding the use of NFV in humans (34). The following is an excerpt of the key features.

VIRACEPT® (nelfinavir mesylate) is an inhibitor of the human immunodeficiency virus (HIV) protease. VIRACEPT Tablets are available for oral administration as a light blue, capsule-shaped tablet with a clear film coating in 250 mg strength (as NFV free base) and as a white oval tablet with a clear film coating in 625 mg strength (as NFV free base). Each tablet contains the following common inactive ingredients: calcium silicate, crospovidone, magnesium stearate, hypromellose, and triacetin. In addition, the 250 mg tablet contains FD&C blue #2 powder and the 625 mg tablet contains colloidal silicon dioxide. VIRACEPT Oral Powder is available for oral administration in a 50 mg/g strength (as NFV free base) in bottles. The oral powder also contains the following inactive ingredients: microcrystalline cellulose, maltodextrin, dibasic potassium phosphate, crospovidone, hypromellose, aspartame, sucrose palmitate, and natural and artificial flavor. The chemical name for nelfinavir mesylate is [3S-[2(2S*, 3S*), 3a,4ab,8ab]]-N-(1,1-dimethylethyl)decahydro-2-[2-hydroxy-3-[(3-hydroxy-2-methylbenzoyl)amino]-4-(phenylthio)butyl]-3-isoquinoline carboxamide mono-methanesulfonate (salt) and the molecular weight is 663.90 (567.79 as the free base). Nelfinavir mesylate has the following structural formula:

Nelfinavir mesylate is a white to off-white amorphous powder, slightly soluble in water at pH 4 and freely soluble in methanol, ethanol, 2-propanol and propylene glycol.

Pharmacokinetics

The pharmacokinetic properties of NFV were evaluated in healthy volunteers and HIV-infected patients; no substantial differences were observed between the two groups.

Absorption: Pharmacokinetic parameters of NFV (area under the plasma concentration-time curve during a 24-hour period at steady-state [AUC24], peak plasma concentrations [Cmax], morning

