6.9 Study Visit Flowchart

7 Statistical Plan

A 28 patient phase II trial of NFV and concurrent chemo/RT with measurements of hypoxia by $^{18}\text{EF-5}$ or FMISO PET imaging and serum biomarkers will be performed. Locoregional control is the primary endpoint, defined from first day of chemo/RT+NFV to local or regional progression. Distant progression and patients free of locoregional control will be censored. The "pre and post-NFV" measurements mentioned below, refer to samples obtained before and after a 7-14 day run-in period of NFV prior to chemo/RT. These pre/post-NFV changes are evaluated as "early change" predictors of treatment outcome. Hypotheses tested by statistical analyses are:

NFV given with chemo/RT will improve locoregional control (primary objective) will be tested by comparing our locoregional control to a historical result by log rank test with adequate power as described below. In a randomized pilot study by Rischin (JCO 24:2098-2104, 2006) in head and neck cancer, patients with hypoxic tumors who received concurrent chemoradiotherapy had a 3-year locoregional control rate of 30%, while patients who received the hypoxia-activating pro-drug tirapazamine and concurrent chemoradiotherapy had a 3-year locoregional rate of 95%. Although the difference in local control was stunning, the sample sizes of these groups was very modest. Therefore, we have powered our study conservatively, in order to detect a more modest treatment effect.

Starting with this amendment, a total of 28 patients will be enrolled over 4 years, assuming a rate of 7 patients per year. To date, only 2 larynx cancer patient had been enrolled on this trial, so 4 years of accrual will be needed to meet the target sample size. We will then follow patients for an additional 6 months. There will be 85% power to detect a 30% absolute increase in 3-year locoregional control from a 40% rate for standard concurrent chemoradiotherapy to 70% for Nelfinavir and concurrent chemoradiotherapy, using a 1-sided log rank test at a 5% type I error rate. Power calculated with SWOG software (http://www.swogstat.org/stat/public/one_nonparametric_survival.htm).

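### The trial is designed around 3-year locoregional control, but the final analysis comes 6 months after the last enrolment, when under even accrual only about 37.5% of patients can have 3 years of follow-up; a later cut-off would be a cheap gain

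*Combined protocol and SAP*

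**What the plan says.** - **Endpoint.** Section 7 makes locoregional control the primary endpoint, "defined from first day of chemo/RT+NFV to local or regional progression", with censoring. It is compared with a historical result by a one-sided log-rank test at 5%.
- **Design effect.** "There will be 85% power to detect a 30% absolute increase in 3-year locoregional control", namely "from a 40% rate for standard concurrent chemoradiotherapy to 70% for Nelfinavir and concurrent chemoradiotherapy".
- **Accrual.** Section 7: "a total of 28 patients will be enrolled over 4 years, assuming a rate of 7 patients per year". Section 4.7 gives a slightly wider range: "With an estimated accrual of 7-8 subjects per year, it is anticipated that accrual will continue for approximately 4 years".
- **Follow-up before analysis.** Section 7: "We will then follow patients for an additional 6 months". Section 4.7 agrees and calls the analysis final: "Patients will then be followed an additional 6 months prior to final statistical analysis".
- **Duration.** The Study Summary gives "Study Duration 5 years".
- **After the 3-month scan.** Section 4.6 takes patients off study at the 3-month PET/CT, with follow-up for toxicity and survival after that. Section 6.8.3 and the follow-up paragraph of Section 9.3 grade toxicity to the first routine visit after radiation and then follow for survival. Section 6.8.3 leaves later imaging to standard of care.

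**The concern.** The effect that the trial is built to detect is expressed at 3 years. Four years of accrual plus 6 months puts the analysis at 4.5 years, so only patients enrolled in the first 1.5 years can have been watched for 3 years. The 3-year rate that readers will set beside the historical figure would come from the sparse end of a Kaplan-Meier curve. At stake are the precision of that rate and some power. Both could be improved with the same 28 patients by waiting longer.

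**Working it through.** **Inputs.** From Section 7: N = 28; accrual A = 4 years; follow-up after the last enrolment F = 0.5 years; 3-year control 40% (null) and 70% (target); one-sided 5%. From Section 4.7: 7 to 8 patients per year. From the Study Summary: 5 years. My assumptions: uniform accrual, exponential failure times, and censoring only by the analysis date. The hazards are −ln(0.4)/3 = 0.305 and −ln(0.7)/3 = 0.119 per year, a ratio of 0.389.

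**1. The plan's own power.** The large-sample Kaplan-Meier standard error at 3 years is

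SE = S(3) × √[(1/N) ∫₀³ λ / (S(u) C(u)) du], with C(u) = min(1, (A + F − u)/A).

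With A = 4 and F = 0.5, SE is 0.1169 under the null and 0.1068 under the target.

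Power = Φ[(0.30 − 1.645 × 0.1169) / 0.1068] = Φ(1.008) = 84%.

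This matches the stated 85%, so that figure already allows for the 6 months.

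**2. Share who can reach 3 years** = (A + F − 3)/A.
- At 7 per year: (4.5 − 3)/4 = 37.5%, or 10.5 of 28.
- At 8 per year, accrual takes 28/8 = 3.5 years: (4.0 − 3)/3.5 = 28.6%, or 8 of 28.
- The endpoint clock starts 7 to 14 days after nelfinavir begins, which lowers 37.5% to about 36.5–37.0% if patients start nelfinavir at enrolment.

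**3. Expected number at risk at 3 years.** At 70% control: 10.5 × 0.7 = 7.4. At 40%: 10.5 × 0.4 = 4.2. Both are before any censoring for distant progression or loss.

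**4. Effect of the cut-off, same 28 patients, 4-year accrual.** The half-width is 1.96 × SE under the target.

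| Months after last enrolment | Share with 3 years possible | At risk at 3 years (70% / 40%) | SE null / target | Landmark power | 95% half-width at 70% |
|---|---|---|---|---|---|
| 6 | 37.5% | 7.4 / 4.2 | 0.1169 / 0.1068 | 84% | 21 points |
| 12 | 50% | 9.8 / 5.6 | 0.1068 / 0.0982 | 90% | 19 points |
| 36 | 100% | 19.6 / 11.2 | 0.0926 / 0.0866 | 96% | 17 points |

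At 8 per year with 6 months of follow-up, the standard errors are 0.1240 and 0.1127, and landmark power is Φ[(0.30 − 1.645 × 0.1240)/0.1127] = 80%.

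**5. The test that Section 7 names.** I simulated a one-sample log-rank test, comparing observed failures with those expected under the 40% hazard (100,000 trials per setting). Type I error is 3.8% at both 6 and 12 months. Power is 89% at 6 months and 93% at 12.

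**6. Calendar.** 4 + 0.5 = 4.5 years; 4 + 1 = 5 years, the stated duration; 4 + 3 = 7 years.

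**The case against.** The strongest reply is that the design already pays for its short follow-up. The 85% includes it, the endpoint is time to event, and patients followed for less than 3 years still contribute to a log-rank test. More follow-up adds precision in almost any trial. All of this stands, and it is why the point is an improvement and not a fault.

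Four stronger readings are tempting, and the documents do not support them.

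- **That the test is anti-conservative.** A reader might infer this from the few patients left at 3 years. An untransformed Kaplan-Meier test at 3 years does run at 6.7% in simulation with 6 months of follow-up. But Section 7 names a log-rank test, which runs at 3.8%. Even a landmark test on the complementary log-log scale holds 4.9%.
- **That 37.5% is a ceiling.** It is the value under even 4-year accrual. Front-loaded or slower accrual would give more, and faster accrual less. Sections 3.2 and 3.3 also report 15 subjects already imaged with EF5. How they relate to the 28 counted from this amendment is unclear.
- **That 6 months of declared study time lies idle.** The Summary does not say what the 5 years covers. The balance may be meant for close-out, and 4.5 years within 5 is not a contradiction.
- **That more calendar time by itself yields more endpoint data.** Sections 4.6, 6.8.3 and 9.3 provide only for survival and toxicity after the 3-month scan, so a later cut-off helps only if locoregional status is also collected.

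It is also fair that 12 months still leaves half the patients short of 3 years and narrows the interval by only 2 points.

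**Conclusion.** The point holds as a low-cost improvement. Neither the stated power nor the named test is wrong on this account. With the final analysis 6 months after the last enrolment, the 3-year rate rests on about 7 patients at risk at the target rate or about 4 at the null rate, with a 95% half-width of about 21 points at 70%. Moving the cut-off to 12 months adds about 5 points of landmark power (84.4% to 89.7%) and about 4 of log-rank power (89% to 93%). A precise 3-year rate needs the later update as well.

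These figures rest on uniform accrual, exponential failure times and no loss to follow-up. Section 7 gives no loss rate. If censoring for distant progression or loss removed 20% of patients by 3 years (my assumption), landmark power would be about 79% at 6 months and 86% at 12. The value of waiting also depends on locoregional status being recorded throughout.

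**What to change.** 1. Set the final analysis 12 months after the last enrolment in Sections 4.7 and 7, and say in the Study Summary what the 5 years covers. If close-out needs the remaining time, lengthen the stated duration.
2. Pre-specify one updated estimate of 3-year locoregional control when every patient has 3 years of potential follow-up. That falls at about 7 years, so the Summary duration must change.
3. State in Sections 4.6, 6.8.3 and 9.3 that locoregional status and the date of last locoregional assessment are recorded from standard-of-care visits after the 3-month PET/CT until the data cut-off.
4. Report the number at risk and a 95% confidence interval with every 3-year estimate.

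No extra patients or study visits are needed. The costs are a final readout 6 months later, continued chart review of routine care, and an update that comes well after the main result.

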5.2 Treatment Regimen

All subjects will begin taking daily oral nelfinavir, at a dose of 1250 mg bid, 7 to 14 days prior to the start of CTRT. At any point during the study, if a patient cannot tolerate swallowing NFV tablets or require PEG for medication administration, then the tablet can be crushed and dissolved in water for consumption orally or via PEG. Directions for dissolving NFV are as follows:

- Place Nelfinavir tablet(s) in small amount of water.
- Once dissolved, mix the cloudy liquid well, and consume it immediately.
- The glass should be rinsed with water and the rinse swallowed to ensure the entire dose is consumed.

Nelfinavir will be continued during the complete course of concurrent CTRT. The 7-14 day window of pre-CTRT nelfinavir is included to allow for imaging with [^{18}F]-FMISO PET/CT and [^{18}F]-FDG PET/CT evaluation to assess for changes in tumor oxygenation and glucose uptake

secondary to NFV. Subjects will be asked to maintain a drug diary to assess compliance with administration of nelfinavir.

5.3 Method for Assigning Subjects to Treatment Groups

The subjects will be identified for this study based on their inclusion/exclusion criteria. Since this is a phase II study, there is no assignment to treatment groups and all subjects are treated as per protocol.

5.4 Preparation and Administration of Study Drug

Nelfinavir will be available in Investigational Drug Services (IDS) at the Hospital of the University of Pennsylvania. When a subject is enrolled, the drug will be obtained from IDS and dispensed in the Department of Radiation Oncology. It is stored at room temperature.

Preparation and administration of [¹⁸F]-FMISO is described in the CMC section.

5.5 Subject Compliance Monitoring

Subject medication compliance will be monitored via 2 mechanisms: 1) a medication diary for Nelfinavir. Subjects will be asked to complete and return the diary each week of their treatment. 2) via Epic med reconciliation (MD attestation of med reconciliation is recorded and tracked within Epic) at the patient's weekly visit with their treatment MD during the course of radiotherapy. If necessary, the subject will be counseled on medication issues. Patients who discontinue the use of Nelfinavir due to side effects will still be followed as a study subject as per the intent to treat analysis.

5.6 Prior and Concomitant Therapy

Any prior therapy is permitted with the exception of radiation therapy to the head and neck (defined as more than 5 fractions and more than 10 Gy) and any standard chemotherapy within the last 5 years.

5.7 Packaging

IDS will package the Nelfinavir specific to each subject in 30 day cycles.

5.8 Receiving, Storage, Dispensing and Return

5.8.1 Receipt of Drug Supplies

Nelfinavir will be bought and stored as needed by Investigational Drug Services.

[¹⁸F]-FMISO will be synthesized at the cyclotron facility of the University of Pennsylvania and delivered to Department of Radiation Oncology in the Perelman Center for Advanced Medicine by a trained Cyclotron team member in single dose vials according to the standard procedures outlined by the Cyclotron Facility. Once the drug has been delivered to the

Department of Radiation Oncology, all standard hospital procedures will apply for handling, processing, and destruction of any residual amounts if applicable. As [¹⁸F]-FMISO is a short-lived radiotracer with a half-life of approximately 110 minutes it will be synthesized for same day use, [¹⁸F]-FMISO will not be stored. The remaining activity in the vials that exists in the lab will be stored only until the activity decays to undetectable level. All vials will be disposed of according to the standard operating procedure set forth by the hospital.

5.8.2 Dispensing of Study Drug

Nelfinavir will be dispensed by the research coordinator while the subject is in clinic.

The [¹⁸F]FMISO dose will be drawn and accurately measured in the dose calibrator in the imaging facility and administered by bolus injection to the patient under the direct supervision of a Nuclear Medicine Authorized User. The injectable dose of [¹⁸F]FMISO for most studies will be \leq 10 mCi (expected range at injection 5 – 10 mCi), a lesser dose may be injected if, in the opinion of a Nuclear Medicine Authorized User complete imaging data could be generated. In the dose of [¹⁸F]FMISO, only some fractions of the FMISO molecules are radioactive. [¹⁸F]-FMISO is administered to subjects by intravenous injection of \leq 10 mL. The injection will be followed by a saline flush. The injection or imaging procedure will be terminated in any patient who exhibits anaphylaxis, significant dyspnea or chest pain.

5.8.3 Return or Destruction of Study Drug

[figure not shown]
Nelfinavir: At the completion of the study, there will be a final reconciliation of drug shipped, drug consumed, and drug remaining. This reconciliation will be logged on the drug reconciliation form, signed and dated. Any discrepancies noted will be investigated, resolved, and documented prior to return or destruction of unused study drug. Drug destroyed on site will be documented by Investigational Drug Services.

[¹⁸F]-FMISO: If the entire study drug dose is administered, the radioactive syringe will be disposed of into the radioactive waste in the Department of Radiation Oncology in the Perelman Center for Advanced Medicine. As the radioactive half-life of ¹⁸F is 1.83 hours, we anticipate that by the end of a working day, the radioactive syringe can be safely disposed of in the standard biologic waste. In the event that the study drug is not administered or only partially administered, the radioactive syringe, vial and the contents will be disposed of in the radioactive waste in the Department of Radiation Oncology in the Perelman Center for Advanced Medicine. It will be subsequently disposed of in the standard biologic waste upon sufficient decay of its radioactivity.

6 Study Procedures

6.1 General study design

Twenty-eight subjects will be enrolled on this clinical trial investigating the efficacy of definitive NFV + CTRT for locally advanced head and neck cancer. Patients will also receive two ¹⁸F-FMISO PET/CT studies: the first at baseline to determine baseline tumor hypoxia and the second after a 7-14 day lead-in of NFV prior to CTRT (to determine change in tumor oxygenation secondary to NFV). Patients will undergo 2 separate ¹⁸F-FDG PET/CT scans: the first at baseline as part of routine clinical care, for purposes of radiation treatment planning and the second after a 7-14 day lead-in of NFV prior to CTRT (to determine change in tumor glucose uptake secondary to NFV). Additionally, blood and serum (two tubes, approximately 15 ml) will be collected for tumor biomarker analysis twice: once at baseline, and again after completion lead-in NFV, prior to CTRT.

Study Schema

6.2 Nelfinavir Administration

All subjects will begin taking daily oral nelfinavir, at a dose of 1250 mg bid, 7 to 14 days prior to the start of CTRT. Nelfinavir will be continued during the complete course of concurrent CTRT. The 7-14 day window of pre-CTRT nelfinavir is included to allow for imaging with ¹⁸F-FMISO and ¹⁸F-FDG PET/CT to assess for changes in tumor oxygenation and glucose uptake secondary to NFV. Subjects will be asked to maintain a drug diary to assess compliance with administration of nelfinavir. Subjects will also undergo weekly med reconciliation of compliance with taking NFV during their scheduled visit with their treating MD during radiotherapy (MD attestation of med reconciliation is recorded and tracked within EPIC).

6.3 Chemotherapy Administration

Standard cisplatin chemotherapy consisting of cisplatin will be administered as concurrent therapy with radiation. Cisplatin 100 mg/m² will be administered on days 1, 22, and 43, with pretreatment and post treatment hydration and a polyantiemetic regimen. Patients may also be treated with either weekly cisplatin or weekly cetuximab, which is another FDA-approved drug shown to be an effective radiosensitizer in the treatment of head and neck cancer (36, 37).

Patients who are receiving cetuximab may receive a loading dose, as per standard of care, prior to their completion of their repeat imaging, if deemed necessary by the treating physician. The treating medical oncologist may make adjustments to the chemotherapy regimen and/or dosing, as they deem medically appropriate. Development of severe dysphagia, dehydration, orthostasis, or other unforeseen grade 4 toxicity is potential grounds for discontinuation of treatment if therapy is delayed longer than 1 week to permit recovery. Should a holiday or hospital closing interfere with the above detailed chemotherapy administration schedule, the medical oncologist will adjust each subjects administration as they see medically appropriate.

